9.2.2. Phase II/III Study with Pause in Enrollment

If a decision of expanding to Phase III study is made at the first interim analysis (IA1) which will occur after 9 months of OS follow-up in the first 300 participants, then this study will be a Phase III study with a total of 640 participants. Thus, 300 and 340 participants will be enrolled before and after IA1, respectively, with an approximate 12 months pause in enrollment between the 2 enrollment phases.

Overall Survival

The final OS analysis is event driven and will be carried out after approximately 425 events have occurred across 2 arms.

The sample size and power calculation of OS are based on the following assumptions:

1. The target hazard ratio is 0.72 at the end of study for OS between the GSK3359609 in combination with pembrolizumab and 5FU/platinum chemotherapy arm and the placebo in combination with pembrolizumab and 5FU/platinum chemotherapy arm
2. OS of the placebo in combination with pembrolizumab and 5FU/platinum chemotherapy arm follows the same distribution as the pembrolizumab + chemotherapy arm in the total population of KN-048 trial. That is, the survival rates at 6, 12, 24 and 36 months are approximately 77%, 53.0%, 29.4% and 22.6%, respectively, with a median survival time of 13 months
3. Enrollment consists of 2 phases. The first phase is an enrollment period of ~15 months for 300 participants, followed by an approximate 12 month pause of enrollment. The second phase is an enrollment period of ~18 months for 340 participants
4. Yearly drop-out rate of 5%

The following alpha- and beta-spending functions are used in the OS hypothesis.

- For the OS hypothesis, the alpha-spending function based on Lan-DeMets O'Brien-Fleming approximation spending function and the futility boundary of p-value > 0.1 at IA1 are constructed to implement group sequential boundaries that control the type I error rate as well as allow for non-binding futility analysis.

The following two OS scenarios were considered as it is expected that one of these scenarios will most likely be observed in 209227 trial.

Scenario 1 – proportional hazards with heavy tail

Scenario 1 assumes the hazard ratio of OS is consistent between the GSK3359609 in combination with pembrolizumab and 5FU/platinum chemotherapy arm and the placebo in combination with pembrolizumab and 5FU/platinum chemotherapy arm with heavy tails for both arms.

Under the proportional hazard assumption with 425 events at the final analysis, this study has 71.2% power to demonstrate superiority of OS at the one-sided alpha level of 2.49% with a true HR of 0.72. If the futility boundary of p-value > 0.1 is not crossed at IA1, there is 98.8% probability to demonstrate superiority of OS with a true HR of 0.72. Success for OS at the final analysis approximately corresponds to an observed hazard ratio of 0.82.

Scenario 2 – non-proportional hazards with delayed separation of OS curve and heavy tail

A simulation study was performed with same piecewise time varying hazard ratios described in Section 9.2.1. The simulation showed the final analysis will be delayed by approximately 3 months compared with the proportional hazard scenario. Under the non-proportional hazard assumption with 425 events at the final analysis, the study has 47.9% power to demonstrate superiority of OS at the one-sided alpha level of 2.49% with a true HR of 0.72 at the final analysis. If the futility boundary of p-value > 0.1 is not crossed at IA1, there is 98.8% probability to demonstrate superiority of OS with a true HR of 0.72. Success for OS at the final analysis approximately corresponds to an observed hazard ratio of 0.82.

Progression-free Survival

The final PFS analysis will be carried out at the time of the second interim analysis (IA2) for OS; with approximately 456 PFS events across the 2 arms. With 456 PFS events, the study has 92% power to demonstrate superiority in PFS when the true hazard ratio for PFS is 0.62 at type I error rate of 0.01% (one-sided).

The sample size and power calculation of PFS is based on the following assumptions:

1. PFS follows an exponential distribution with a median of 5 months in the placebo in combination with pembrolizumab and platinum-based chemotherapy arm
2. Hazard ratio is 0.62 for PFS between the GSK3359609 in combination with pembrolizumab and 5FU/platinum chemotherapy arm and the placebo in combination with pembrolizumab and 5FU/platinum chemotherapy arm
3. Enrollment consists of 2 phases. The first phase is an enrollment period of ~15 months for 300 participants, followed by a 12 month pause in enrollment. The second phase is an enrollment period of ~18 months for 340 participants
4. Yearly dropout rate of 10%

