9.5. Interim Analyses

If the study continues as a Phase III study, there will be two interim analyses on OS, allowing for early stopping of the study due to efficacy or allow for non-binding futility analysis.

For the Phase III study with no enrollment pause, the timing of the two interim analyses will be triggered by the pre-specified number of OS events in the total population. The final analysis of PFS will be aligned with the first OS interim analysis.

For the Phase II/III study with an enrollment pause, the first interim analyses of OS (IA1, adaptive decision making) will occur when the first 300 participants have a minimum follow-up of 9 months. A futility criterion of p-value > 0.1 for log-rank test of OS is pre-specified for adaptive decision making. If the futility criterion is not met at the first interim analysis (IA1), the study will continue as a Phase III study and enrollment of an additional 340 participants to a total of 640 participants will occur. If the futility criterion is met in the OS analysis, the study will stop for futility. The timing of the second interim

analyses will be triggered by the pre-specified number of OS events in the total population. The final analysis of PFS will be aligned with the second OS interim analysis.

The nominal significance levels for the interim and final analyses of OS will be determined by the Lan-DeMets spending function based upon the O'Brien-Fleming boundary. The futility bounds of this study are non-binding and the bounds are considered guidance rather than strict bounds.

[Table 13](#) and [Table 14](#) summarizes the required number of events, sample size and decision guidance for the planned PFS and OS analyses for the 2 Phase III study scenarios, respectively. Efficacy boundaries and non-binding futility boundaries are based on initially assigned type I error rate before any alpha re-allocation and projected number of events at study mile stones. The actual boundaries will be determined from the actual number of interim analyses conducted and from the actual number of events, at the time of the specified interim analysis using the alpha- and beta- spending functions. Actual futility bounds will be updated if overall beta is changed with respect to alpha reallocation.

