Table 5 and Table 6 summarize the required number of events, sample size and decision guidance for the planned PFS and OS analyses for the two Phase III study scenarios, respectively. Efficacy boundaries and non-binding futility boundaries are based on initially assigned type I error rate before any alpha re-allocation and projected number of events at study milestones. The actual boundaries will be determined from the actual number of interim analyses conducted and from the actual number of events, at the time of the specified interim analysis using the alpha- and beta- spending functions. Actual futility bounds will be updated if overall beta is changed with respect to alpha reallocation.

Results of the interim analyses will be reviewed by an independent data monitoring committee (IDMC). Further details of interim analyses are provided in the IDMC Charter. Any change to the planned event size will be described in the statistical analysis plan before any unblinding of the data except in the event of early study termination.

Due to early study termination, no interim analyses will be performed.

Table 5 Summary of Number of Events, Sample Size and Decision Guidance at the Planned Interim and Final Analyses for Phase III Study with no Pause in Enrollment

Analysis	Key Endpts	Expected Number of Events at the Planned Analysis (Information Fraction)	Efficacy Boundary ¹		Non-binding Futility Boundary ¹	
			p-value	Cumulative Alpha	p-value	Cumulative Beta
IA1 : Final PFS Analysis (H3, H4), Interim OS Analysis 1 (H1, H2)	PFS	~470 (100%)	0.0001	0.0001	NA	NA
	OS	~310 (76%)	0.01	0.01	0.619	0.0007
IA2 : Interim OS Analysis 2 (H1, H2)	OS	~375 (92%)	0.0016	0.019	0.143	0.017
FA : Final OS Analysis (H1, H2)	OS	~410 (100%)	0.019	0.0249	0.019	0.094

Abbreviations: Endpts=endpoints; FA: final analysis; H=hypothesis; IA: interim analysis; NA: not applicable; PFS=progression-free survival; OS=overall survival

1. Efficacy boundaries and non-binding futility boundaries are based on initially assigned type I error rate (one-sided) before any alpha roll-over and projected number of events at study milestones. Actual efficacy boundaries will be based on the actual number of interim analyses conducted and actual numbers of events available at study milestones. Actual futility bounds will be updated if overall beta is changed with respect to alpha roll-over.

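### Two printed group-sequential figures contradict the documents' own tables: 98.8% conditional OS success (protocol 9.2.2, Scenario 1) should be 96.6%, and the IA2 efficacy p-value of 0.0016 (SAP Table 5) should be 0.016

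*Protocol*

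**What the plan says.** **Design with an enrolment pause (protocol 9.2.2, Table 14; SAP Table 6).** Under Scenario 1 (proportional hazards) the protocol states: "this study has 71.2% power to demonstrate superiority of OS at the one-sided alpha level of 2.49% with a true HR of 0.72". The next sentence reads: "If the futility boundary of p-value > 0.1 is not crossed at IA1, there is 98.8% probability to demonstrate superiority of OS". Table 14 gives, for OS:

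| Look | Events | Efficacy p | Futility p | Cumulative beta |
|---|---|---|---|---|
| IA1 | 136 | 0.00007 | 0.1 | 0.263 |
| IA2 | 315 | 0.009 | NA | 0.263 |
| Final | 425 | 0.022 | 0.022 | 0.288 |

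Scenario 2 (delayed separation) prints the same 98.8%, although there "the study has 47.9% power to demonstrate superiority of OS at the one-sided alpha level of 2.49% with a true HR of 0.72".

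**Design without a pause (protocol Table 13; SAP Table 5).** Both tables give 375 OS events and cumulative alpha 0.019 at IA2, with futility p 0.143 and cumulative beta 0.017. The efficacy p-value is the only entry in the row that differs: 0.016 in the protocol, 0.0016 in the SAP.

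**How the figures are used.** Protocol 9.5 sets the expansion rule: "A futility criterion of p-value > 0.1 for log-rank test of OS is pre-specified for adaptive decision making". SAP 4.7 says of the printed boundaries: "The actual boundaries will be determined from the actual number of interim analyses conducted". It also says: "Due to early study termination, no interim analyses will be performed".

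**The concern.** The 98.8% is a conditional probability, so it is fixed by two numbers that the protocol also prints: the overall power and the chance of stopping at IA1. It does not follow from them. It overstates how safe the Phase III expansion would be once IA1 is passed.

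The 0.0016 is an efficacy threshold for a primary endpoint. The SAP disagrees with the protocol on it. It is also stricter than the IA1 level of 0.01, whereas O'Brien-Fleming-type nominal levels rise from look to look at these event counts. Anyone applying Table 5 literally would need a much larger observed effect to declare success at IA2.

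**Working it through.** **Inputs.** One-sided alpha 0.0249, true HR 0.72 and the futility rule p > 0.1 at IA1 (protocol 9.2.2); 1:1 allocation (9.2); Lan-DeMets O'Brien-Fleming spending (9.2.1, 9.2.2, 9.5). Events are 136/315/425 with the pause (Table 14) and 310/375/410 without it (Table 13).

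**Method.** The Z statistics are taken as multivariate normal with mean sqrt(d/4) × |ln 0.72| at d events and correlation sqrt(d_i/d_j). Efficacy bounds come from the spending function.

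**1. Reproduce the pause design.**

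- Nominal p: 0.00007 / 0.0092 / 0.0221 (printed 0.00007 / 0.009 / 0.022).
- Critical HR at the final analysis: 0.823 (printed 0.82).
- Mean Z at IA1: sqrt(136/4) × 0.3285 = 1.915. The futility bound is Z < 1.2816, so P(stop) = 0.263 (printed 0.263).
- Overall power: 0.712 (printed 71.2%).

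Everything printed for this scenario reproduces except the conditional probability.

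**2. Conditional success, Scenario 1.** Success requires passing IA1, so P(success | IA1 passed) = power / (1 − beta at IA1).

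- From the printed figures: (1 − 0.288)/(1 − 0.263) = 0.712/0.737 = 0.966.
- Allowing for rounding of both betas: from (1 − 0.2885)/(1 − 0.2625) = 0.965 to (1 − 0.2875)/(1 − 0.2635) = 0.967.
- By integration without intermediate rounding: 0.7123/0.7369 = 0.967.
- For 98.8% to be right, overall power would have to be 0.988 × 0.737 = 72.8% (beta 0.272). That contradicts both 71.2% and 0.288.

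Other readings do not rescue it. A Freedman-type mean gives 96.5%, counting success at the final look only gives 96.3%, and a single final test at the full alpha gives 96.8%. A 10,000-trial log-rank simulation with the stated control curve, accrual, pause and dropout gives 96.5%.

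**3. IA2 without the pause.** Spending at 310/375/410 events gives:

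| | IA1 | IA2 | Final |
|---|---|---|---|
| Nominal p | 0.0099 | 0.0161 | 0.0188 |
| Cumulative alpha | 0.0099 | 0.0190 | 0.0249 |

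This matches protocol Table 13, and power comes out at 90.6%, as stated in 9.2.1. With 0.0016 at IA2, cumulative alpha there is only 0.0101, so SAP Table 5 contradicts its own row.

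If 0.0016 had been applied literally, with the IA1 and final bounds unchanged:

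| | IA2 p = 0.0161 | IA2 p = 0.0016 |
|---|---|---|
| Critical HR at IA2 | 0.80 | 0.74 |
| Success by IA2 at HR 0.72 | 85.9% | 73.3% |
| Overall power | 90.6% | 89.9% |
| Alpha used (one-sided) | 2.49% | 2.22% |

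**4. Scenario 2.** Table 14 carries no beta for this scenario, so the same check is not possible. With 47.9% power, 98.8% implies a probability of passing IA1 of 0.479/0.988 = 48.5%, which only the sponsor's simulation can confirm.

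**The case against.** Neither arithmetic error is disputable. The case on the other side concerns weight and scope.

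- **No decision uses either number.** This stands. Expansion depends on p > 0.1. The printed bounds rest on projected events and were to be replaced by actual ones. The SAP now rules out interim analyses. The 0.0016 is exposed by its own row and, taken literally, is conservative.
- **96.6% is a quotient of rounded entries; unrounded integration gives 96.7%.** True, but the difference is rounding. 96.6% is what the printed tables imply, and neither value is near 98.8%.
- **The loss of overall power from 0.0016 assumes that the final bound stays put.** This is right. If the alpha left unspent at IA2 were recovered at the final look, the final nominal p would be 0.0220 and overall power 90.9%. Only the lower chance of success by IA2 follows from the misprint itself.
- **Scenario 2 shows no discrepancy.** Correct: it is a question, not an error. A simulation of Scenario 2 gave 98.7%, which would fit the same value having been printed in both paragraphs. But it produced 57% power rather than 47.9%, and about 149 IA1 events rather than 136, so it proves nothing.
- **The HR of 0.72 in Scenario 2 is already explained.** Partly. The section's first assumption ties 0.72 to the end of the study, and the Scenario 2 power sentence refers to the final analysis. The conditional-probability sentence carries no such qualifier, and neither says how 0.72 summarises hazard ratios of 1, 0.69, 0.52 and 0.50.

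**Conclusion.** Both figures are wrong as written. The Scenario 1 conditional success is 96.6%, not 98.8%. This overstatement of 2.2 percentage points follows from the printed 71.2% power and IA1 beta of 0.263 alone. The SAP's IA2 efficacy p-value is ten times too small: 0.016 is the value that agrees with the protocol, the spending function and the cumulative alpha of 0.019. This rests on the printed event counts and on proportional hazards with HR 0.72, the setting that reproduces the other printed values.

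The consequence is confined to the record. Event numbers, the stated 71.2% and 90.6% power, and the expansion rule are unaffected. The Scenario 2 figure remains unverified rather than wrong.

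**What to change.** - Protocol 9.2.2, Scenario 1: replace 98.8% with 96.6%.
- SAP Table 5, IA2 row: replace 0.0016 with 0.016.
- Protocol 9.2.2, Scenario 2: check 98.8% against the existing simulation output. In the two sentences that cite an HR of 0.72, say what that value summarises when the hazard ratio changes over time.

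The cost is two one-line edits, one look-up in existing output and a short clarification. One stated probability becomes slightly less favourable; no analysis changes.

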9.3. Populations for Analyses

The following populations are defined:

Population	Description
All Screened	All participants who sign the ICF
Intent-to-treat	All randomized participants whether or not randomized intervention was administered This population will be based on the study intervention to which a participant was randomized and will be the primary population for the analysis of efficacy data.
Safety	All randomized participants who take at least 1 dose of study intervention. This population will be the primary population for the analyses of safety data.
Pharmacokinetic	The Pharmacokinetic Population will consist of those participants in the Safety Population from whom at least 1 PK sample has been obtained and analysed. This population will be the primary population for PK analyses.

9.4. Statistical Analyses

The statistical analysis plan will be finalized prior to first patient first visit and it will include a more technical and detailed description of the statistical analyses described in this section. This section provides summary of the planned statistical analyses of the most important endpoints including primary and key secondary endpoints.

9.4.1. Primary and secondary endpoints will be included in the main CSR. A separate final CSR will report updated key safety analyses at the end of study. Further details will be outlined in the statistical analysis plan.

Efficacy Analyses

The intent-to-treat (ITT) population that includes all randomized participants will serve as the primary population for the efficacy analyses. The hypotheses on OS and PFS will be tested at significance levels as specified in Section 9.8. All confidence intervals will be estimated at 95% significance level.

Stratified statistical analyses will be based on the following stratification factors, PD-L1 expression (CPS ≥ 20 vs. $1 \leq$ CPS < 20 vs. CPS < 1), and HPV status (positive vs. negative). Participants with oropharynx HPV negative/unknown and non-oropharyngeal tumors will be combined as the HPV negative group in the stratified analyses. Details will be documented in the statistical analysis plan.

An outline of the analysis strategy for key efficacy endpoints is presented in [Table 9](#). Details are outlined in Section [9.4.1.1](#) and Section [9.4.1.2](#) and will be further delineated in the statistical analysis plan.

Table 9 Analysis Strategy for Key Efficacy Endpoints

Endpoint	Statistical Method ¹	Analysis Population	Missing Data Approach
OS	Test: Stratified log-rank test to assess the treatment difference Estimation: Stratified Cox model with Efron's tie handling method to assess the magnitude of treatment difference	ITT	Model based 
 • Censoring rule(s)
PFS per RECIST v1.1	Test: Stratified log-rank test to assess the treatment difference Estimation: Stratified Cox model with Efron's tie handling method to assess the magnitude of treatment difference	ITT	Model based 
 • Censoring rule(s)
ORR/DCR per RECIST v1.1	Stratified Miettinen and Nurminen's method with sample size weights	ITT	Participants with missing data are considered non-responders and conservatively included in denominator
Duration of Response per RECIST v1.1	Summary statistics using Kaplan-Meier method	All Responders in ITT	Non-responders are excluded from analysis

Abbreviations: DCR=disease control rate; ITT=intent-to-treat; ORR=overall response rate; OS=overall survival; PFS=progression-free survival; RECIST= Response Evaluation Criteria in Solid Tumors

Statistical models are described in further detail in the statistical analysis plan.

Statistical analyses of PFS, ORR, DCR, and duration of response per iRECIST follow similarly.

9.4.1.1. Primary Analyses

Overall Survival

OS is defined as the interval of time from the date of randomization to the date of death due to any cause. Participants without documented death will be censored at last known alive date.

The non-parametric Kaplan-Meier method will be used to estimate the survival curves. The treatment difference in survival will be assessed by the stratified log-rank test. A stratified Cox proportional hazard model with Efron's method of tie handling will be used to assess the magnitude of the treatment difference (i.e., the hazard ratio). The hazard ratio and its 95% confidence interval from the stratified Cox model with a single treatment covariate will be reported. OS rate at 12 months, 24 months, 36 month and the corresponding 95% CI will also be estimated from the Kaplan-Meier analysis.

The Restricted Mean Survival Time (RMST) method or piecewise HR method may be conducted as appropriate to account for the possible non-proportional hazards effect.

Additional analyses of OS adjusting for the effect of subsequent treatment may be performed based on recognized methods, e.g., the Rank Preserving Structural Failure Time (RPSFT) model [Robins, 1991], if a sufficient proportion of participants switch. The choice of the method will be based on an examination of the appropriateness of the data to the assumptions required by the method. To further account for the possible confounding effect, a supplementary analysis of OS censoring participants at the time of initiation of new therapy will be performed.

The proportional hazards assumption will be assessed using graphical method and testing the interaction term of treatment and time in the Cox model. More details will be provided in the statistical analysis plan.

Progression-Free-Survival per RECIST v1.1

Progression-free-survival (PFS) per RECIST v1.1 is defined as the time from the date of randomization to the date of the first documented disease progression per RECIST v1.1 based on investigator assessment, or death due to any cause, whichever occurs first.

A summary of the assignments for progression and censoring dates for the primary analysis of PFS per RECIST v1.1 is specified in Table 10. Supplementary analyses of PFS per RECIST v1.1 with different censoring rules will be delineated in the statistical analysis plan.

Table 10 Censoring Rules for Primary Analysis of PFS per RECIST v1.1

Situation	Primary Analysis
No baseline disease assessments and the participant has not died	Censored at the date of randomization
No post-baseline disease assessments and the participant has not died	Censored at the date of randomization
With post-baseline disease assessments, new anticancer treatment is not initiated and no documented PD or death	Censored at the date of last adequate radiological disease assessment ¹
With post-baseline disease assessments and new anticancer treatment is initiated (prior to documented PD or death) ²	Censored at the date of last adequate radiological disease assessment on or prior to the initiation of new anticancer treatment
PD or death documented after ≤ 1 missed disease assessment	Progressed at the date of documented PD ³ or death
PD or death documented after ≥ 2 missed disease assessments	Censored at the date of last adequate radiological disease assessment prior to the ≥ 2 missed disease assessment

Abbreviations: CR=complete response; PD=progressive disease; PFS=progression-free survival; PR=partial response; RECIST=response evaluation criteria in solid tumors; SD=stable disease

1. An adequate assessment is defined as an assessment where the investigator assessed response is CR, PR, or SD.
2. If PD and new anti-cancer therapy occur on the same day, it is assumed that the progression was documented first (i.e. outcome is progression; the date is the date of the assessment for progression).
3. The earliest of (i) Date of radiological assessment showing new lesion (if progression is based on new lesion); or (ii) Date of radiological assessment showing unequivocal progression in non-target lesions, or (iii) Date of last radiological assessment of measured lesions (if progression is based on increase in sum of measured lesions).

The non-parametric Kaplan-Meier method will be used to estimate the PFS curves. The treatment difference in PFS will be assessed by the stratified log-rank test. A stratified Cox proportional hazard model with Efron's method of tie handling will be used to assess the magnitude of the treatment difference (i.e., hazard ratio) between the treatment arms. The hazard ratio and its 95% confidence interval from the stratified Cox model with Efron's method of tie handling and with a single treatment covariate will be reported.

The proportional hazards assumption will be assessed using graphical method and testing the interaction term of treatment and time in the Cox model. In case the proportional hazards assumption is not valid for PFS, the RMST method or piecewise HR as appropriate may be performed for PFS to account for the possible non-proportional hazards effect. Details will be provided in the statistical analysis plan.

